## 7. Study population

Male and female subjects with documented newly diagnosed multiple myeloma who meet all of the eligibility criteria in Section 7.1.1 below will be enrolled into the study.

#### 7.1. Inclusion and exclusion criteria

Subjects are to be assessed for suitability for entry into the study based on the following inclusion and exclusion criteria.

#### 7.1.1. Inclusion criteria

Subjects must meet all of the following inclusion criteria to be eligible for enrollment into the study:

- 1. Understand and voluntarily sign an informed consent form.
- 2. Age  $\geq$ 65 years or not eligible for high dose therapy and autologous stem cell transplant.
- 3. Able to adhere to the study visit schedule and other protocol requirements.

Page 27 of 86 Confidential

4. Diagnosed with multiple myeloma and be considered to have active disease. Patients must not have received an active chemotherapy regimen or Dexamethasone. Patients may have received palliative radiotherapy at least 2 weeks prior to the study start.

- Measurable myeloma paraprotein levels in serum (≥ 0.5 g/dL), urine (≥ 0.2 g excreted in a 24-hour urine collection sample) or by serum free light chains (involved free light chain greater than 100mg/L)
- 6. Eastern Cooperative Group (ECOG) Performance Status of 0 or 1.
- Serum bilirubin levels ≤1.5 times the upper limit of the normal range for the laboratory (ULN).
- 8. Serum AST or serum ALT] levels  $\leq 2 \times \text{ULN}$
- 9. Must have adequate bone marrow function:
  - a. Absolute neutrophil count  $> 1,000 \text{ cells/mm}^3 (1.0 \text{ x } 10^9/\text{L}).$
  - b. Platelets  $\geq 100,000 \text{ /mm}^3$ .
- 10. Hemoglobin > 8 g/dL
- 11. Must have adequate renal function: Renal function assessed by calculated creatinine clearance as follows (see Appendix VI: Cockcroft-Gault estimation of CrCl):
  - a. Calculated creatinine clearance ≥ 30ml/min by Cockcroft-Gault formula. See section below, "Prescribing Information", regarding lenalidomide dose adjustment for calculated creatinine clearance ≥ 30ml/min and < 60ml/min.
- 12. Low risk myeloma is defined as the absence of the following adverse features[21]
  - i. t(4;14) by FISH or metaphase cytogenetics
  - ii. t(14,16) or t(14;20) by FISH or metaphase cytogenetics
  - iii. Deletion 17q13 by FISH
  - iv. Deletion 13 by metaphase analysis
  - v. Aneuploidy by metaphase analysis

Page 28 of 86 Confidential

- vi. B2 microglobulin > 5.5
- 13. Able to tolerate one of the following thromboprophylactic strategies: aspirin, low molecular weight heparin or warfarin (coumadin).
- 14. All study participants must be registered into the mandatory RevAssist® program, and be willing and able to comply with the requirements of RevAssist®.
- 15. Females of childbearing potential (FCBP)† must have a negative serum or urine pregnancy test with a sensitivity of at least 50 mIU/mL within 10 14 days and again within 24 hours prior to prescribing lenalidomide for Cycle 1 (prescriptions must be filled within 7 days) and must either commit to continued abstinence from heterosexual intercourse or begin TWO acceptable methods of birth control, one highly effective method and one additional effective method AT THE SAME TIME, at least 4 weeks before she starts taking lenalidomide. FCBP must also agree to ongoing pregnancy testing. Men must agree to use a latex condom during sexual contact with a female of child bearing potential even if they have had a successful vasectomy. See Appendix VIII: Risks of Fetal Exposure, Pregnancy Testing Guidelines and Acceptable Birth Control Methods.

#### 7.1.2. Exclusion criteria

The presence of any of the following will exclude a subject from study enrollment:

- 1. Ongoing severe infection requiring intravenous antibiotic treatment.
- 2. Life expectancy of less than 3 months.

<sup>† A female of childbearing potential is a sexually mature female who: 1) has not undergone a hysterectomy or bilateral oophorectomy; or 2) has not been naturally postmenopausal for at least 24 consecutive months (i.e., has had menses at any time in the preceding 24 consecutive months).

Page 29 of 86 Confidential

- 3. Performance status of 2, 3 or 4
- 4. Prior malignancy, except for adequately treated basal cell or squamous cell skin cancer, in-situ cervical cancer, or other cancer from which the subject has been disease-free for at least 2 years.
- 5. Solitary bone or solitary extramedullary plasmacytoma as the only evidence of plasma cell dyscrasia.
- 6. Uncontrolled medical problems such as diabetes mellitus, congestive heart failure, coronary artery disease, hypertension, unstable angina, arrhythmias), pulmonary, hepatic and renal diseases unless renal insufficiency is felt to be secondary to multiple myeloma.
- 7. Any serious medical condition, laboratory abnormality, or psychiatric illness that would prevent the subject from signing the informed consent form.
- 8. Pregnant or lactating females.
- 9. Any condition, including the presence of laboratory abnormalities, which places the subject at unacceptable risk if he/she were to participate in the study or confounds the ability to interpret data from the study.
- 10. Known hypersensitivity to thalidomide.
- 11. Use of any other experimental drug or therapy within 28 days of baseline.
- 12. The development of erythema nodosum if characterized by a desquamating rash while taking thalidomide or similar drugs.
- 13. Any prior use of lenalidomide.
- 14. Concurrent use of other anti-cancer agents or treatments.
- 15. Known seropositive for or active viral infection with human immunodeficiency virus (HIV), hepatitis B virus (HBV) or hepatitis C virus (HCV). Patients who are seropositive because of hepatitis B virus vaccine are eligible.

Page 30 of 86 Confidential

## 8. Treatments

## 8.1.1. Investigational drug and reference therapy

## **8.1.1.1.** Supplier(s)

Celgene Corporation will supply Revlimid® (lenalidomide) to study participants at no charge through the RevAssist® program. All physicians who prescribe lenalidomide for research subjects enrolled into this trial and all research subjects enrolled into this trial must be registered in and must comply with all requirements of Celgene's RevAssist® program.

Commercial supplies of dexamethasone, prednisone, low molecular weight heparin, coumadin and aspirin will be used for this study.

## 8.1.1.2. Lenalidomide Description

REVLIMID® (lenalidomide), a thalidomide analogue, is an immunomodulatory agent with antiangiogenic properties. The chemical name is 3-(4-amino-1-oxo 1,3-dihydro -2*H*-isoindol-2-yl) piperidine-2,6-dione and it has the following chemical structure:

#### **Chemical Structure of Lenalidomide**

3-(4-amino-1-oxo 1,3-dihydro-2*H*-isoindol-2-yl) piperidine-2,6-dione

The empirical formula for lenalidomide is  $C_{13}H_{13}N_3O_3$ , and the gram molecular weight is 259.3.

Page 31 of 86 Confidential

Lenalidomide is an off-white to pale-yellow solid powder. It is soluble in organic solvent/water mixtures, and buffered aqueous solvents. Lenalidomide is more soluble in organic solvents and low pH solutions. Solubility was significantly lower in less acidic buffers, ranging from about 0.4 to 0.5 mg/ml. Lenalidomide has an asymmetric carbon atom and can exist as the optically active forms S(-) and R(+), and is produced as a racemic mixture with a net optical rotation of zero.

## Clinical pharmacology

#### **Mechanism of Action:**

The mechanism of action of lenalidomide remains to be fully characterized. Lenalidomide possesses immunomodulatory and antiangiogenic properties. Lenalidomide inhibited the secretion of pro-inflammatory cytokines and increased the secretion of anti-inflammatory cytokines from peripheral blood mononuclear cells. Lenalidomide inhibited cell proliferation with varying effectiveness (IC50s) in some but not all cell lines. Of cell lines tested, lenalidomide was effective in inhibiting growth of Namalwa cells (a human B cell lymphoma cell line with a deletion of one chromosome 5) but was much less effective in inhibiting growth of KG-1 cells (human myeloblastic cell line, also with a deletion of one chromosome 5) and other cell lines without chromosome 5 deletions. Lenalidomide inhibited the expression of cyclooxygenase-2 (COX-2) but not COX-1 in vitro.

## Pharmacokinetics and Drug Metabolism:

#### **Absorption:**

Lenalidomide, in healthy volunteers, is rapidly absorbed following oral administration with maximum plasma concentrations occurring between 0.625 and 1.5 hours post-dose.

Page 32 of 86 Confidential

Co-administration with food does not alter the extent of absorption (AUC) but does reduce the maximal plasma concentration (Cmax) by 36%. The pharmacokinetic disposition of lenalidomide is linear. Cmax and AUC increase proportionately with increases in dose. Multiple dosing at the recommended dose-regimen does not result in drug accumulation.

Pharmacokinetic analyses were performed on 15 multiple myeloma patients treated in the phase I studies. Absorption was found to be rapid on both Day 1 and Day 28 with time to maximum blood levels ranging from 0.7 to 2.0 hours at all dose levels (5mg, 10mg, 25mg, and 50mg). No plasma accumulation was observed with multiple daily dosing. Plasma lenalidomide declined in a monophasic manner with elimination half-life ranging from 2.8 to 6.1 hours on both Day 1 and 28 at all 4 doses. Peak and overall plasma concentrations were dose proportional over the dosing range of 5mg to 50mg. Exposure (AUC) in multiple myeloma patients is 57% higher than in healthy male volunteers.

#### **Pharmacokinetic Parameters:**

## **Distribution:**

In vitro (14C)-lenalidomide binding to plasma proteins is approximately 30%.

#### **Metabolism and Excretion:**

The metabolic profile of lenalidomide in humans has not been studied. In healthy volunteers, approximately two-thirds of lenalidomide is eliminated unchanged through urinary excretion. The process exceeds the glomerular filtration rate and therefore is partially or entirely active. Half-life of elimination is approximately 3 hours.

Page 33 of 86 Confidential

## Dosage form

Lenalidomide will be supplied as capsules for oral administration. Lenalidomide will be supplied as 5 mg and 25 mg capsules for oral administration.

## **Prescribing Information**

Lenalidomide (Revlimid®) will be provided to research subjects for the duration of their participation in this trial at no charge to them or their insurance providers. Lenalidomide will be provided in accordance with the RevAssist® program of Celgene Corporation. Per standard RevAssist® requirements all physicians who prescribe lenalidomide for research subjects enrolled into this trial, and all research subjects enrolled into this trial, must be registered in and must comply with all requirements of the RevAssist® program. Prescriptions must be filled within 7 days. Only enough lenalidomide for one cycle of therapy will be supplied to the patient each cycle.

The planned dose of lenalidomide for investigation is 25 mg/day, orally on days 1 - 21 followed by 7 days rest (28 day cycle). Dosing will be based on CrCl:

Lenalidomide will be given at a dose of 25 mg once daily on days 1 to 21, every 28 days for those patients with a subjects with a creatinine clearance of  $\geq$  60 mL/min by Cockroft-Gault formula.

Subjects with a creatinine clearance of  $\geq$  30 mL/min but < 60 mL/min by Cockroft-Gault formula will begin lenalidomide at 10 mg once daily on days 1 to 21, every 28 days. The lenalidomide dose may be increased to dose 15 mg at the start of Cycle 3 if hematologic

toxicities have not occurred.

Page 34 of 86 Confidential

Dosing will be in the morning at approximately the same time each day. Lenalidomide capsules should be swallowed whole, and should not be broken, chewed or opened.

If a dose of lenalidomide is missed, it should be taken as soon as possible on the same day. If it is missed for the entire day, it should not be made up.

Patients who take more than the prescribed dose of lenalidomide should be instructed to seek emergency medical care if needed and contact study staff immediately.

## **Special Handling Instructions**

Females of childbearing potential should not handle or administer lenalidomide unless they are wearing gloves.

## 8.1.1.3. Study Drug Storage

## **Lenalidomide**

Lenalidomide should be stored at room temperature away from direct sunlight and protected from excessive heat and cold.

## Dexamethasone and prednisone

Dexamethasone should be stored at room temperature away from direct sunlight and protected from excessive heat and cold.

#### 8.1.1.4. Record of administration

Subjects will receive diary cards to record when medications are taken. Diary cards will be collected at the end of each cycle or every 3 cycles in maintenance.

Page 35 of 86 Confidential

Accurate records will be kept in the source documents of all drug administration (including prescribing and dosing). After April 2016, diary card will no longer be used

#### Dexamethasone

Commercial dexamethasone is available as 4 mg tablets for oral administration.

## Prednisone

Commercial prednisone is available as 50 mg tables for oral administration

Low Molecular Weight Heparin, Coumadin or Aspirin:

Commercial low molecular weight heparin, coumadin or aspirin for oral administration will be utilized.

## 8.1.2. Treatment assignments

Subjects will be entered in to the study sequentially in the order they are registered.

## **8.1.3.** Prior/Concomitant therapy

All medications (prescription and non-prescription), treatments and therapies taken from 28 days prior to the start of study drug, Lenalidomide, through to the last dose of study drug, must be recorded on the appropriate page of the data collection system. Subjects will be supplied a diary to record their concomitant medications. After April 2016, diary card will no longer be used.

## **8.1.3.1.** Allowed concomitant therapy

The use hematopoietic growth factors for subjects in this study are permitted when used to treat neutropenia and anemia. In addition, low dose prednisone (up to 10 mg/day) may be used for the treatment and prevention of lenalidomide induced neutropenia. Therapies considered necessary

Page 36 of 86 Confidential

for the subject's well being may be administered at the discretion of the Investigator. These therapies may include bisphosphonates, palliative radiation therapy, antibiotics, analgesics, antihistamines, or other medications as well as transfusions of red blood cells, platelets, or fresh frozen plasma given to assist in the management of complications associated with multiple myeloma. Low dose corticosteroid therapy, (the equivalent up to 10 mg a day of prednisone) for the treatment of the patient existing autoimmune, rheumatologic or inflammatory conditions is allowed.

## 8.1.3.2. Prohibited concomitant therapy

Concomitant use of other anti-myeloma therapy while the subject is on study drug is prohibited.

No new investigational therapies shall be initiated while the subject is on study drug.

# 8.1.4. Treatment compliance

To monitor treatment compliance, reconciliation of Lenalidomide capsules will be done at each study visit. Subject diaries will be provided to assist in the collection of dosing information between study visits. After April 2016, diary card will no longer be used and reconciliation of lenalidomide capsule will not be performed.

#### **8.1.5.** Dose modification or interruption

Subjects will be evaluated for adverse events at each visit using the National Cancer Institute Common Toxicity Criteria (NCI CTCAE) version 4.0 to grade severity. All subjects who are discontinued due to an adverse event should be followed for as long as necessary to document the resolution or stabilization of the event.

#### 8.1.5.1. Dose Reduction Steps for Lenalidomide

Page 37 of 86 Table 1: Lenalidomide dose levels Confidential

Page 38 of 86 Confidential

Starting Dose	Dose level –1	Dose Level -2	Dose Level -3	Dose Level -4
25 mg PO days	15 mg PO days	10 mg PO days	5 mg PO days 1-	Discontinue
1-21 of a 28 days	1-21 of a 28 days	1-21 of a 28 days	21 of a 28 days	
cycle	cycle	cycles	cycles	

Lenalidomide dose reductions will be done as per the instruction below and as illustrated in the following example.

Example 1: A patient is being treated with lenalidomide 25mg daily on Days 1-21 every 28 days and requires a lenalidomide dose reduction per Table 1. The patient will start their next cycle of therapy with lenalidomide 15 mg daily on Days 1-21 every 28 days.

Lenalidomide will always be dosed daily on Days 1-21 every 28 days. The minimum lenalidomide dose is 5 mg/day on days 1-21 every 28 days. If this dose is not tolerated, lenalidomide must be discontinued.

**Table 2: Dose Modification Guidelines for Lenalidomide** 

CTCAE CATEGORY	CTCAE	TREATMENT ADJUSTMENT
ADVERSE EVENT	GRADE	Maintenance Phase
Neutropenia	Grade 3 with	Hold lenalidomide for remainder of cycle
	fever	if the toxicity occurs in the latter 2 weeks
	grade 4	of the cycle and resume the next cycle at
		the dose detailed below. Alternatively if
		the toxicity occurred during the first 2

Page 39 of 86 Confidential

		weeks of the cycle, then hold lenalidomide
		until the toxicity improves to $\leq$ grade 2
		and resume lenalidomide as detailed
		below.
		First occurrence: when resolved to ≤ grade
		2 begin next cycle with one dose level
		reduction of lenalidomide or continue
		same dose with cytokine or low dose
		prednisone support.
		Second occurrence: when resolved to ≤
		grade 2 begin next cycle with one level
		dose reduction of lenalidomide or
		continue same dose with cytokine support
		if not already implemented.
		Subsequent dose reductions of
		lenalidomide are permitted at the
		investigators discretion.
Thrombocytopenia	Grade 4	Hold lenalidomide for remainder of cycle
		if the toxicity occurs in the latter 2 weeks
		of the cycle and resume the next cycle
		with one dose level reduction in
		lenalidomide. Alternatively if the toxicity
		occurred during the first 2 weeks of the

Page 40 of 86 Confidential

		cycle, then hold lenalidomide until the
		toxicity improves to ≤ grade 2 and resume
		lenalidomide with one dose level
		reduction
Cardiac toxicity	Arrhythmia≥	Hold lenalidomide until resolved to ≤
	grade 2	grade 1. Resume at one dose level
		reduction of lenalidomide.
	Arrhythmia≥	Discontinue protocol therapy.
	grade 3	
	Congestive	Discontinue lenalidomide at the
	heart failure >	investigators discretion.
	grade 2	
Hyperthyroidism/	Any grade	Hold lenalidomide and evaluate patient.
Hypothyroidism		May resume therapy at the same dose
		once patient is stable at investigators
		discretion.

Page 41 of 86 Confidential

Non desquamating rash	Grade 2	Hold lenalidomide for remainder of cycle
		if the toxicity occurs in the latter 2 weeks
		of the cycle and resume the next cycle
		with one dose level reduction in
		lenalidomide if the toxicity resolves to less
		than grade 2. Alternatively if the toxicity
		occurred during the first 2 weeks of the
		cycle, then hold lenalidomide until the
		toxicity improves to < grade 2 and resume
		lenalidomide with one dose level
		reduction
	Grade 3 or 4	Discontinue protocol therapy.
Desquamating rash or Erythema	Any grade	Discontinue protocol therapy.
Multiforme		

Page 42 of 86 Confidential

Allergic reaction or	Grade 2 or 3	Hold lenalidomide for remainder of cycle
hypersensitivity		if the toxicity occurs in the latter 2 weeks
		of the cycle and resume the next cycle
		with one dose level reduction in
		lenalidomide if the toxicity improves to
		less than grade 2. Alternatively if the
		toxicity occurred during the first 2 weeks
		of the cycle, then hold lenalidomide until
		the toxicity improves to less than grade 2
		and resume lenalidomide with one dose
		level reduction.
	Grade 4	Discontinue lenalidomide
Venous thrombosis/embolism	≥ Grade 3	Hold (interrupt) dose, consider therapeutic
		anticoagulation; restart at investigator's
		discretion (maintain dose level)

Page 43 of 86 Confidential

Other non-hematologic toxicity	Grade 3 / 4	Hold lenalidomide for remainder of cycle
except those events specifically		if the toxicity occurs in the latter 2 weeks
attributed to dexamethasone as		of the cycle and resume the next cycle
outlined in table 4.		with one dose level reduction in
		lenalidomide. Alternatively if the toxicity
		occurred during the first 2 weeks of the
		cycle, then hold lenalidomide until the
		toxicity improves to ≤ grade 2 and resume
		lenalidomide with one dose level
		reduction.

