#### **DOSING REGIMENS:**

- Oral Lenalidomide (R) will be administered every 28 days as follows:
  - 25 mg QD PO daily on Days 1-21 followed by 7 days rest (10 mg dose will be used for patients with a Creatinine clearance < 60 ml/min)
- Oral Prednisone (100 mg) will be administered on days 1 to 5 of every 28 days cycle in patients receiving combination lenalidomide and prednisone (LP).
- Oral dexamethasone (40 mg) will be administered once a week in patients receiving lenalidomide and low dose dexamethasone (Ld).

All subjects will also receive concomitant aspirin 81 mg PO daily. For patients who cannot tolerate aspirin, low molecular weight heparin or therapeutic doses of coumadin may be used in place of aspirin.

#### Rationale for Amendment 6

MCC16018 has enrolled 30 patients from 2/2010 to 6/2013. It has been closed to accrual since 10/2013 given it met its accrual target. Currently, six patients only continue on treatment, for now 2-4 years. We anticipate to final close the study as soon as a manuscript has been published. Of note, lenalidomide was approved by the FDA for newly diagnosed multiple myeloma patients in 2/2015. MCC16018 involves lenalidomide based therapy for newly diagnosed multiple myeloma and is thus currently considered standard of care (although that use was considered investigational at the time of initiation and completion of accrual of the study). Accordingly, we propose to collect more limited data pertaining to the current treatment of study subject as of 2/2016 until the final closure of the trial. Specifically, we will only plan to capture only serious adverse events (SAE), response and follow up data. Patients will continue on treatment and undergo standard of care monitoring which is at the discretion of the treating physician.

The changes made with this amendment will serve several purposes:

- 1- Decrease the burden on patients to comply with study requirement (for example, comply with study visit timeframe).
- 2- Decrease the number of deviations due to non-compliance with study requirements (such as missed 24h urine protein electrophoresis, laboratory testing outside the window).
- 3- Decrease the burden to the study team which would otherwise continue to collect additional data which will not aid in the overall interpretation of the study results (it is unlikely that a new toxicity to lenalidomide will be encountered in this study population that have been on this treatment for now 2-4 years on average)

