## 4.2.4 Adverse Events

Most frequently reported adverse events reported during clinical studies with lenalidomide in oncologic and non-oncologic indications, regardless of presumed relationship to study medication include: anemia, neutropenia, thrombocytopenia and pancytopenia, abdominal pain,

Page 18 of 86 Confidential

nausea, vomiting and diarrhea, dehydration, rash, itching, infections, sepsis, pneumonia, UTI, Upper respiratory infection, atrial fibrillation, congestive heart failure, myocardial infarction, chest pain, weakness, hypotension, hypercalcemia, hyperglycemia, back pain, bone pain, generalized pain, dizziness, mental status changes, syncope, renal failure, dyspnea, pleural effusion, pulmonary embolism, deep vein thrombosis, CVA, convulsions, dizziness, spinal cord compression, syncope, disease progression, death not specified and fractures.

Complete and updated adverse events are available in the Investigational Drug Brochure and the IND Safety Letters.

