#### **8.1.7.** Discontinuation from treatment

The following events are considered sufficient reasons for discontinuing a subject from study drug:

- Subject declines further study participation.
- Adverse event(s) (AEs) that, in the judgment of the Investigator, may cause severe or permanent harm or which rule out continuation of study drug.

Page 48 of 86 Confidential

- Major violation of the study protocol.
- Progression of disease/unsatisfactory therapeutic effect

Page 49 of 86 Confidential

- Death
- Pregnancy or a positive pregnancy test
- Discontinuation of lenalidomide for any reason
- Subject lost to follow-up
- If for any other reason, must be specified in the data collection system.

Study Closure

Reasons for discontinuation should be recorded in the data collection system and in the subject's medical records.

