# 9. Safety assessments

The following safety assessments will be done at baseline and at scheduled intervals throughout the duration of the study (see Section 2, Schedule of Study Assessments). Unless otherwise noted, all laboratory testing will be conducted in the local laboratory. After April 2016, safety assessments will not be mandated by the trial but rather will be at the discretion of the treating physician in accordance with standard of care management of multiple myeloma patients on lenalidomide.

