9.7.4. Efficacy assessments

9.7.4.1. Myeloma paraprotein

Serum and urine protein electrophoresis, quantitative immunoglobulins, serum and urine

immunofixation studies (see Section 2, Schedule of Study Assessments). Response will

be assessed using the Uniform response criteria set forth by the International myeloma

working group (IMWG) (See Appendix II). Response will be assessed at least every 3

months in the maintenance setting.

Version. 6 date 4/15/2016

Page 56 of 86 Confidential As of April 2016, given all patients are in maintenance, patients will be followed for follow up and survival. Response assessment is not mandated per the trial and per institutional standard of care and to occur at a minimum of every 3 months.

Page 57 of 86 Confidential

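### Table 2's two arrhythmia rows overlap, so a grade 3 or 4 arrhythmia is told both to resume lenalidomide at a lower dose and to stop protocol therapy

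*Combined protocol and SAP*

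**What the plan says.** Table 2 in section 8.1.5.1 gives the lenalidomide dose changes by toxicity and CTCAE grade. Cardiac toxicity has two arrhythmia rows:

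- **Arrhythmia ≥ grade 2:** hold lenalidomide until the event has resolved to at most "grade 1. Resume at one dose level" reduction.
- **Arrhythmia ≥ grade 3:** "Discontinue protocol therapy".

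Two other toxicities in the table also have a hold row and a discontinue row separated by grade. Non-desquamating rash is held at grade 2 and ends protocol therapy at grade 3 or 4. Allergic reaction is held at grade 2 or 3, and at grade 4 the instruction is "Discontinue lenalidomide".

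Two other sections bear on the decision. Section 8.1.6 allows a new cycle once a therapy-related arrhythmia has come down to grade 1 or less; that criterion lapses after April 2016. Section 8.1.7 lists among the reasons for stopping study drug adverse events that, "in the judgment of the Investigator, may cause severe or permanent harm" or rule out continuing it.

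**The concern.** The first arrhythmia row has no upper limit, so read literally it includes the grades that the second row assigns to discontinuation. An investigator facing a grade 3 or 4 arrhythmia has one line that leads back to treatment at a reduced dose and another that ends protocol therapy.

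What is at stake is whether a patient is re-exposed to lenalidomide after a severe arrhythmia. The event is foreseeable: section 4.2.4 lists "atrial fibrillation, congestive heart failure, myocardial infarction" among the adverse events reported with the drug, and the trial enrols older adults. The reading also decides whether the patient stays on protocol therapy and whether re-treatment would count as a protocol deviation. Investigators should not have to infer the answer.

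**Working it through.** No statistical figure is involved, so the check compares the grades each row covers and then looks for text that settles any overlap.

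**Step 1. Grades covered by each pair of rows.** The inputs are the grade entries in Table 2. Grades 1 to 4 are considered, because a decision to resume or stop arises only there.

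| Toxicity | Hold row | Discontinue row | Grades in both |
|---|---|---|---|
| Arrhythmia | {2, 3, 4} | {3, 4} | {3, 4} |
| Non-desquamating rash | {2} | {3, 4} | none |
| Allergic reaction | {2, 3} | {4} | none |

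Two of the three grades in the arrhythmia hold row therefore carry two incompatible actions; only grade 2 is unambiguous. One of the three pairs overlaps and two do not.

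**Step 2. Search for a rule of precedence.**

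- Sections 8.1.5 and 8.1.5.1 do not say that the stricter row governs.
- Section 8.1.6 made no exception for an arrhythmia that had earlier reached grade 3 or 4. Until April 2016 it was therefore compatible with restarting after such an event.
- Section 8.1.7 allows stopping on the investigator's judgment but does not choose between the rows.

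None of these resolves the overlap.

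**Step 3. Remaining reach.** The Amendment 6 rationale in the synopsis gives 30 enrolled patients and states: "Currently, six patients only continue on treatment, for now 2-4 years". The largest share of Moffitt patients a correction could still reach is 6/30 = 20%. The documents give no arrhythmia rate, so an expected number of affected patients cannot be calculated.

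**Step 4. Does Table 2 still apply to those patients?** Other provisions carry an explicit April 2016 end date, for example diary cards and capsule counts (8.1.4), the new-cycle criteria (8.1.6) and concomitant therapy (9.5). Table 2 carries none. Its action column is headed for the maintenance phase, and section 9.7.4.1 says "As of April 2016, given all patients are in maintenance". Against this, section 9 says that after that date "safety assessments will not be mandated by the trial", and sections 8.1.6 and 8.2 leave new cycles and follow-up to the treating physician. No text switches the table off, but its practical force after April 2016 is open to argument.

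**Step 5. Effect on the analysis.** Section 12.2.3 lists events of grade 3 or higher, and serious adverse events, separately. An arrhythmia of that severity in the collected data would be reported under either reading. The sample size (12.1) and the 12-month PFS analysis (12.2.1) do not use Table 2.

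**Step 6. After the correction.** With the first row limited to grade 2, the arrhythmia sets become {2} and {3, 4}. They share no grade, every grade from 2 to 4 still has an action, and the pattern matches the rash rows.

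**The case against.** The strongest reply is that the table has only one sensible reading. If the first row governed grades 3 and 4, the second row would never apply. Only the stepped reading gives both rows an effect, the stricter row stands directly below, and the rash and allergic-reaction rows follow the same stepped form. Most investigators would probably stop treatment at grade 3, and nothing in the documents shows that anyone did otherwise. This carries weight: it makes the intent fairly clear and keeps the point minor. It does not make the wording correct, because the reader must still supply a precedence rule that the protocol omits.

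A second reply is that little remains to correct. Accrual ended in June 2013, six patients remain, care after April 2016 is largely discretionary, and the synopsis expects final closure once a manuscript is published. This also stands as a limit on importance. The heading on Table 2's action column is weak evidence that the table remains in force: taken literally it would exclude the first six cycles from the only lenalidomide toxicity table, which is implausible. The firmer ground is that no text ends the table's use.

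A third reply is that the overlap rests on one symbol in a table extracted from PDF. A misread cannot be fully excluded. However, the symbol appears in both arrhythmia rows, while the rash row came through as a plain grade 2, and nothing points to an extraction error.

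**Conclusion.** The concern holds. As written, Table 2 gives two incompatible instructions for grade 3 and grade 4 arrhythmia, and no other section says which to follow. It is best described as an internal inconsistency in an operative safety rule, probably a one-symbol slip, with a stepped rule the likely intent.

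The weight is low. At most 6 of 30 Moffitt patients (20%) could still be affected, and continued use of Table 2 for them after April 2016 is arguable. No sample size, endpoint or analysis result changes. The conclusion assumes that the extracted symbol matches the source document and that no precedence rule exists outside the text supplied.

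**What to change.** In Table 2, change the grade entry in the first arrhythmia row from ≥ grade 2 to grade 2, and leave the second row as it is. Grade 2 then means hold and resume one dose level lower; grade 3 or higher means discontinue protocol therapy.

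The change needs no new data, visits or patients. Section 10.1 requires IRB/EC approval before any amendment is implemented, so given the small remaining reach the correction can be carried in the next amendment and does not need one of its own.
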